1.1 Null hypothesis

There is no difference in visual outcome between children with perinatal brain injury when prescribed near vision spectacles compared with the current standard care – waiting until a problem is detected.

*** This null hypothesis is not being formally tested by this exploratory feasibility trial

1.2 Study aim

This study aims to establish the feasibility and acceptability of conducting a randomised controlled trial to test the effectiveness of early near vision correction with spectacles in infancy, for babies, at risk of visual dysfunction.

1.3 Study design:

This is an exploratory, single-centre randomised parallel-group feasibility clinical trial in babies at risk of cerebral visual impairment. The “treatments” under comparison in this study are:

1.3.1 Group A (control arm): First assessments at 8 weeks corrected gestational age (CGA). No glasses prescribed.

1.3.2 Group B1 (intervention arm): First assessments at 8 weeks CGA. Add+3.00DS to the full cycloplegic refraction and prescribe for full-time wear.

1.3.3 Group B2 (intervention arm): First assessments at 16 weeks CGA. Add+3.00DS to the full cycloplegic refraction and prescribe for full-time wear.

Effectiveness of early spectacle intervention on visual outcomes in babies at risk of cerebral visual impairment: a parallel group, open-label, randomised clinical feasibility trial (Babies in Glasses BIG)

1.4 Schedule of assessments

TIMEPOINT**	STUDY PERIOD					
	Enrolment	Allocation	Post-allocation			Close-out
	$-t_1$	0	t_1	t_2	t_3	T_4
ENROLMENT:						
Eligibility Screen	X					
Informed consent	X					
Severe Refractive Error Screen	X					
CSRI Form			X	X	X	X
Demographics Questionnaire	X					
Allocation		X				
INTERVENTIONS:						
Group A						
Group B1						
Group B2						
ASSESSMENTS:						
Ocular assessment			X	X	X	X
Neurodevelopmental assessment				X	X	
fbNIRS			X	X	X	X
Non-serious/ Serious Adverse Event Form	As Needed Throughout Protocol					
Progress notes	X	X	X	X	X	X
Communication log	Every phone or in-person contact outside of regular visits					

CSRI = Client Service Receipt Inventory; fbNIRS = functional broadband near infrared spectroscopy

Effectiveness of early spectacle intervention on visual outcomes in babies at risk of cerebral visual impairment: a parallel group, open-label, randomised clinical feasibility trial (Babies in Glasses BIG)

Effectiveness of early spectacle intervention on visual outcomes in babies at risk of cerebral visual impairment: a parallel group, open-label, randomised clinical feasibility trial (Babies in Glasses BIG)

2. Outcome measures

2.1 Primary outcome measure (feasibility)

The acceptance of randomisation measured by the proportion of recruited parents who accept the offer of randomisation.

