The target sample of eligible babies is pragmatic as we estimate 100 (approximately 35 with hypoxic ischaemic encephalopathy [HIE] and 70 pre-term [<29 weeks]) babies will come through the University College Hospitals London (UCLH) neonatal intensive care unit per year. For feasibility studies, sample sizes between 12 and 50 per group [1], [2] have been recommended to estimate a chosen parameter. We predict 75% acceptance rate resulting in approximately 25 participants in each arm (A, B1, B2). Selecting a sample of 100 from a population and determining that 75% of subjects would agree to recruitment would give 95% confidence that between 65% and 83% of subjects in the population would agree to recruitment. This would provide enough confidence to proceed to a subsequent definitive randomised controlled trial (RCT).

4. Randomisation

The research optometrist will enrol and randomise participants using 'Sealed Envelope', an online randomisation service. Allocation concealment will be ensured, as randomisation will not be carried out until the patient has been recruited into the trial. This ensures that the assignment schedule is unpredictable.

Participants will be randomly assigned to one of three arms, Group A, B1 or B2, with a 1:1:1 allocation as per a computer-generated randomisation schedule stratified by diagnosis (HIE or pre-term) using random permuted blocks.

5. Statistical Data Analysis

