5.1. Analysis Principles

5.1.1 ITT or PP: Analyses will be in accordance with the intention-to-treat (ITT) principle where all patients are analysed as per the groups to which they are randomised and not per-protocol (PP), to retain the validity of the randomisation process.

5.1.2 Significance levels of tests: All statistical tests will use a 2-sided p-value of 0.05, unless otherwise specified. All confidence intervals presented will be 95% and two-sided.

5.1.3 Baseline comparability: Baseline characteristics will be summarised by randomised group and diagnosis. Summary measures for the baseline characteristics of each group will be mean and standard deviation for continuous (approximate) normally distributed variables, medians and interquartile ranges for non-normally distributed variables, and frequencies and percentages for categorical variables. Where numbers are small, we may simply report raw data.

5.1.4 Adjustment for design factors: Since randomisation was stratified by diagnosis (HIE or pre-term) analyses of outcomes will also be stratified.

5.1.5 Follow-up and losses to follow-up: missing data: It is inevitable that some patients will be lost to follow-up. Sample size estimation assumed 10% of patients would not provide an evaluable 6-month outcome. If this rate is observed, data for many patients will be only partially observed. Reasons for missingness may be important and these will be examined. This is a feasibility study and imputation for missing data will not be conducted.

5.2 Planned Analysis:

5.2.1 Primary Analysis: We will report the proportion of participants who accept the offer of randomisation as a proportion with a 95% confidence interval computed by the exact binomial method.

Effectiveness of early spectacle intervention on visual outcomes in babies at risk of cerebral visual impairment: a parallel group, open-label, randomised clinical feasibility trial (Babies in Glasses BIG)

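### The primary outcome is defined among recruited parents, but the trial is sized on agreement to recruitment among about 100 eligible babies

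*SAP*

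**What the plan says.** - SAP 2.1, the primary outcome: "The acceptance of randomisation measured by the proportion of recruited parents who accept the offer of randomisation". The denominator is recruited parents.
- SAP 5.2.1, the primary analysis: "We will report the proportion of participants who accept the offer of randomisation as a proportion with a 95% confidence interval". The interval is to be exact binomial. This describes who is counted as accepting. It does not say out of whom.
- SAP section 3, the sizing: "The target sample of eligible babies is pragmatic as we estimate 100". An acceptance rate of 75% is predicted, giving about 25 babies in each of three arms. The precision statement takes 75% agreement in 100 subjects, and claims that this "would give 95% confidence that between 65% and 83% of subjects in the population would agree to recruitment". The section treats this as sufficient ground for moving on to a definitive trial.
- SAP section 4, the sequence: "randomisation will not be carried out until the patient has been recruited into the trial".
- SAP 1.4, the schedule: informed consent is in the enrolment column, and allocation is a separate, later column.

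**The concern.** In section 3, being recruited is the event that is counted. In 2.1, being recruited is the condition for entering the denominator. One trial cannot report both under one name.

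The families who say most about whether randomisation is acceptable are those who decline when trial entry is offered. Under 2.1 they are never recruited, so they drop out of the calculation. What remains is mostly parents who have already consented to a randomised trial.

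This is the sole primary outcome, and section 3 ties the case for a definitive trial to its precision. Dummy Table 3 will set observed results against progression criteria. An analyst who follows 2.1 and one who follows section 3 could report clearly different headline figures from the same families.

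**Working it through.** **Inputs (all from the SAP).** Eligible babies N = 100 and predicted acceptance 75% (section 3); three arms, allocated 1:1:1 (section 4); two-sided 95% intervals (5.1.2); exact binomial method (5.2.1).

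**Formula.** For x acceptances out of n, the exact (Clopper-Pearson) limits are:
- lower = 0.025 quantile of Beta(x, n − x + 1)
- upper = 0.975 quantile of Beta(x + 1, n − x)
- when x = n, the lower limit is 0.025^(1/n) and the upper limit is 1

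**Step 1: reproduce the plan's figures.** 0.75 × 100 = 75 recruited, and 75/3 = 25 per arm, as stated. The exact interval for 75/100 is 65.3% to 83.1%, which rounds to the stated 65% to 83%. Wilson (65.7% to 82.5%) and Wald (66.5% to 83.5%) do not round to both limits. Section 3 is therefore correct for its own quantity, by the method named in 5.2.1. Its components, 35 and 70, sum to 105 rather than 100; 79/105 gives 65.9% to 83.1%, so this makes no practical difference.

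**Step 2: write out the two quantities.** Let N families be offered entry, r be recruited, and d of those later refuse randomisation.
- Section 3: r/N
- Section 2.1: (r − d)/r

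The families who decline at consent number N − r, here 100 − 75 = 25. They appear in the first quantity and not in the second.

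**Step 3: apply both to the plan's own trial.** Section 3 places all 75 recruited babies in an arm (3 × 25 = 75), which implies d = 0. The non-zero values of d below are assumptions, given to show the range.

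| Reading | x/n | Estimate | Exact 95% interval |
|---|---|---|---|
| Section 3 | 75/100 | 75.0% | 65.3% to 83.1% |
| 2.1, d = 0 | 75/75 | 100% | 95.2% to 100% |
| 2.1, d = 1 | 74/75 | 98.7% | 92.8% to 99.97% |
| 2.1, d = 3 | 72/75 | 96.0% | 88.8% to 99.2% |
| 2.1, d = 5 | 70/75 | 93.3% | 85.1% to 97.8% |

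Even with five refusals after consent, the lower limit (85.1%) lies above the upper limit of the section 3 interval (83.1%).

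**Step 4: can the 75% be moved to the 2.1 denominator?** 0.75 × 75 = 56.25, so about 56 of 75. The interval is 63.3% to 84.0%, close to the stated one, but 56/3 = 18.7 babies per arm, which contradicts the planned 25. The wording of 2.1, the 25 per arm and the 75% agree only if recruited means approached, and section 3 uses recruitment for those who say yes.

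**The case against.** The best reply is that this is loose wording. The acceptance rate in section 3 echoes the acceptance of randomisation in 2.1, and 75% of 100 leads straight to the arm sizes. The authors probably meant one quantity, acceptance among those approached. The protocol may also define who counts as recruited. Both are plausible, but neither reconciles the SAP's own sections, and if the reply is right the correction is short.

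Some stronger readings are tempting and are not supported:

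- **That the outcome must be 100%, or could never show randomisation to be unacceptable.** Section 2.1 treats recruitment and acceptance of randomisation as separate events, and 1.4 separates enrolment from allocation, so a parent could consent and then refuse. The sentence in section 4 concerns allocation concealment; it fixes the order and does not say that recruited parents have already accepted. A value near 100% is an inference from that order and from section 3's arithmetic.
- **That 5.2.1 adds a third denominator.** It names those who accept and states no denominator. It reads as shorthand for 2.1.
- **That infants failing the severe refractive error screen would be miscounted as refusals.** The SAP lists consent and this screen in the same enrolment column and does not say how failures are counted.
- **That multiple births make the interval materially too narrow.** The SAP gives no figure on multiple births from which to judge this.

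**Conclusion.** The SAP defines its primary outcome on one denominator and sizes it on another. With the plan's own numbers, the section 3 quantity is 75% (65.3% to 83.1%). The quantity worded in 2.1 would be expected at about 93% to 100% if between none and five of the 75 recruited families later refuse. That is 18 to 25 percentage points higher, and the intervals do not overlap. The stated 65% to 83% precision does not belong to the outcome as defined, and families who decline at consent would be left out of it.

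The mismatch itself is in the text and needs no assumption. The size rests on two: that recruited in 2.1 means those who agreed, as section 3 uses the word, and that few families refuse between consent and allocation. The conclusion is drawn from the SAP alone. It should be settled before analysis because it decides the headline result.

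**What to change.** In 2.1 and 5.2.1, state one definition:

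- Denominator: families of eligible infants who were offered trial entry, including randomisation.
- Numerator: those among them who agreed to be randomised, with each family classified by its decision.
- Interval: exact binomial, as already planned.
- Secondary figure: randomised over recruited, which shows any refusal after consent.

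Families who agreed but whose infant later fails the refractive screen should stay counted as accepting and be shown separately. Removing them would take out accepters only and bias the rate downwards. For example, with 100 approached, 75 agreeing and an assumed 5 screen failures, the rate would fall from 75/100 = 75% to 70/95 = 73.7%.

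Section 3 can then stand: its 65% to 83% applies to the primary outcome, approximately so if families rather than babies are counted.

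The costs are a less favourable headline proportion, the need to count every family approached, and a check of the new wording against the protocol so that the two documents do not diverge.

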2.2 Secondary outcome measures

Feasibility

2.2.1 The feasibility of fitting and dispensing glasses with varying refractive corrections to infants aged 8 weeks versus 16 weeks CGA

2.2.2 Compliance with spectacle wear for parents and infants when dispensed at 8 weeks and 16 weeks CGA.

2.2.3 The retention rate in all 3 arms, which will be reported descriptively on our CONSORT flow diagram. (This is a change to the published protocol which stated it would be reported by the median number of infants reported per month as it was agreed by investigators that this was likely to confuse readers).

2.2.4 The proportion of families completing phone questionnaire on spectacle compliance as a percentage of those in the intervention groups (B1 & B2).

Clinical

2.2.5 The distribution of visual acuity at the 3 and 6-month follow ups compared with visual acuity at the first visit in all 3 arms.

2.2.6 The distribution of refractive outcomes (measured in dioptres) at 3 and 6-month follow ups as compared to the first visit in all 3 groups.

2.2.7 The distribution of accommodative outcomes (measured in dioptres) at 3 and 6-month follow ups as compared to the first visit in all 3 groups.

2.2.8 Evidence of impaired emmetropisation following administration of intervention. This will be monitored carefully on a case-by-case basis for each child.

2.2.9 The absence of harm through mechanical trauma from prescribing glasses at these ages. This will be monitored carefully on a case-by-case basis for each child.

2.2.10 The distribution of ABCDEFV scores at baseline, 3 and 6 months. Each subtest will be scored as a binary pass fail and these will be totalled (possible 0-14).

Economic

2.2.10. Determination of appropriate resource-use data collection methods. A targeted paediatric Client Service Receipt Inventory (CSRI) form has been modified for this population and will be used for the duration of the feasibility study.

Effectiveness of early spectacle intervention on visual outcomes in babies at risk of cerebral visual impairment: a parallel group, open-label, randomised clinical feasibility trial (Babies in Glasses BIG)

3 Sample size calculation

The target sample of eligible babies is pragmatic as we estimate 100 (approximately 35 with hypoxic ischaemic encephalopathy [HIE] and 70 pre-term [<29 weeks]) babies will come through the University College Hospitals London (UCLH) neonatal intensive care unit per year. For feasibility studies, sample sizes between 12 and 50 per group [1], [2] have been recommended to estimate a chosen parameter. We predict 75% acceptance rate resulting in approximately 25 participants in each arm (A, B1, B2). Selecting a sample of 100 from a population and determining that 75% of subjects would agree to recruitment would give 95% confidence that between 65% and 83% of subjects in the population would agree to recruitment. This would provide enough confidence to proceed to a subsequent definitive randomised controlled trial (RCT).

4. Randomisation

The research optometrist will enrol and randomise participants using 'Sealed Envelope', an online randomisation service. Allocation concealment will be ensured, as randomisation will not be carried out until the patient has been recruited into the trial. This ensures that the assignment schedule is unpredictable.

Participants will be randomly assigned to one of three arms, Group A, B1 or B2, with a 1:1:1 allocation as per a computer-generated randomisation schedule stratified by diagnosis (HIE or pre-term) using random permuted blocks.

5. Statistical Data Analysis

5.1. Analysis Principles

5.1.1 ITT or PP: Analyses will be in accordance with the intention-to-treat (ITT) principle where all patients are analysed as per the groups to which they are randomised and not per-protocol (PP), to retain the validity of the randomisation process.

5.1.2 Significance levels of tests: All statistical tests will use a 2-sided p-value of 0.05, unless otherwise specified. All confidence intervals presented will be 95% and two-sided.

5.1.3 Baseline comparability: Baseline characteristics will be summarised by randomised group and diagnosis. Summary measures for the baseline characteristics of each group will be mean and standard deviation for continuous (approximate) normally distributed variables, medians and interquartile ranges for non-normally distributed variables, and frequencies and percentages for categorical variables. Where numbers are small, we may simply report raw data.

5.1.4 Adjustment for design factors: Since randomisation was stratified by diagnosis (HIE or pre-term) analyses of outcomes will also be stratified.

5.1.5 Follow-up and losses to follow-up: missing data: It is inevitable that some patients will be lost to follow-up. Sample size estimation assumed 10% of patients would not provide an evaluable 6-month outcome. If this rate is observed, data for many patients will be only partially observed. Reasons for missingness may be important and these will be examined. This is a feasibility study and imputation for missing data will not be conducted.

5.2 Planned Analysis:

5.2.1 Primary Analysis: We will report the proportion of participants who accept the offer of randomisation as a proportion with a 95% confidence interval computed by the exact binomial method.

Effectiveness of early spectacle intervention on visual outcomes in babies at risk of cerebral visual impairment: a parallel group, open-label, randomised clinical feasibility trial (Babies in Glasses BIG)

5.2.2 Secondary Endpoint Analysis

Summary statistics will be provided for all secondary outcome measures by treatment group and diagnosis. Summary measures will be mean and standard deviation for continuous (approximately) normally distributed variables, medians and interquartile ranges for non-normally distributed variables, and frequencies and percentages for categorical variables. Treatment differences may be estimated and estimates presented with 95% confidence intervals where appropriate. Where numbers within groups are too small for meaningful summaries patient listings by time point will be tabulated. Scatter graphs will also be included.

5.3 Toxicity / Symptoms

The number of new serious complications occurring before the end of six months will be reported by treatment and diagnosis group.

6. Health Economic Analysis

6.1 Aim and objective of economic analysis

The aim is to assess the feasibility of calculating the incremental cost per unit benefit of providing spectacles compared with treatment as usual in the control arm in a future full RCT, from the perspective of the NHS and Personal Social Services (PSS).

The objective of this feasibility study is to determine and pilot appropriate resource-use data collection methods for a future full RCT. A targeted paediatric CSRI form has been designed specifically for this population and will be used in this feasibility study.

6.2 Reporting of resource use and cost information

Descriptive statistics will be reported for resource use items and their levels of completion, and for costs calculated from these, by randomised group and by diagnosis, and no formal comparisons across groups will be made.

Resource use information will be collected via the resource use questionnaire developed for this feasibility study based on the Client Service Receipt Inventory (CSRI).

Standard unit costs for NHS and PSS (but not productivity losses) will be applied to resource items and these will also be reported descriptively, by randomised group and by diagnosis.

Resource use items or categories will be summarised as frequencies and percentages, and costs will be summarised as means and standard deviations (as this is the format required for summing costs), and medians and interquartile ranges and max-min ranges (as the costs are not usually normally distributed, so this format can be more informative).

The CSRI includes use of health and social care services by trial participants over the follow-up period of the trial, including hospital visits and admissions, accident and emergency (A&E) attendances, outpatient appointments, primary and community services, and medications, either via the NHS or where costs are borne privately by families.

Effectiveness of early spectacle intervention on visual outcomes in babies at risk of cerebral visual impairment: a parallel group, open-label, randomised clinical feasibility trial (Babies in Glasses BIG)

The feasibility of obtaining data on the cost of the intervention itself will also be assessed, and reported as estimated costs of providing the intervention, by randomised group and by diagnosis.

Information was also collected on time off work by the parents or other carers and this will also be reported as descriptive statistics (number of days), as it would be used in a future full trial to assess productivity losses.

6.3 Consideration of effectiveness data (no further analysis here)

A future full trial would require collection of effectiveness (benefit) data, and this feasibility study allows consideration of what type of effectiveness data would be most appropriate in this future context.

To explain further: the standard measurement of benefit for a health economic analysis would use patient-reported information on quality of life, but this is not feasible in this very young population, so clinical measures would instead be used as effectiveness measures for a future health economic analysis.

Previous studies by one of the study co-applicants ([name]) have demonstrated the importance of developmental acceleration of improvement in visual acuity in infancy and by one year of age and across the preschool years [3], [4]

A number of possible effectiveness outcomes will be considered during the feasibility study, in line with the consideration of which is the most appropriate primary outcome to use in the main trial. Possibilities therefore include, but are not limited to: (i) improvement in visual acuity at 6 months compared to visit one, (ii) improvement in accommodation or refraction at 6 months compared to visit one, or (iii) improvement in defined visual developmental milestones at 6 months compared to the first visit.

The incremental cost-effectiveness ratio (ICER) in a future full trial would then be expressed in terms of “incremental cost per unit improvement in clinical outcome”, rather than in the more standard “incremental cost per additional quality-adjusted life-year (QALY) gained” which is often used in studies with older children and adults where quality of life data are collected, either directly from participants or via proxy.

These measures are covered in the statistical part of the analysis as described above, and possible use of these measures as future health economic effectiveness measures will be discussed as part of the reporting for this feasibility study.

Effectiveness of early spectacle intervention on visual outcomes in babies at risk of cerebral visual impairment: a parallel group, open-label, randomised clinical feasibility trial (Babies in Glasses BIG)

7. Appendices - Dummy tables

Table 1: Baseline characteristics of the study patients by treatment and diagnostic group (HEI or pre-term)

Table 2: Ocular characteristics at baseline of the study patients by treatment and diagnostic group (HEI or pre-term)

